3 OVERALL STUDY DESIGN AND PLAN

3.1 Study design

This study is a prospective, multicenter, open-label, non-comparative, long-term extension of the Phase 3 confirmatory core study.

Subjects who have completed the 108-week treatment period in the core study will be enrolled into one group treated with ponesimod 20 mg o.d. Based on anticipated discontinuation rates in the core study, approximately 800 subjects are expected to enter the extension study.

The study will be conducted in approximately 160 sites in 28 countries.

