3.2.3 Treatment period

The treatment period starts with the first dose of study treatment, which defines Day 1 of the extension study. All post-dose assessments of Visit 1 will be conducted during the treatment period.

Ideally, all assessments and procedures of Visit 1, including first study treatment dosing and post-dose cardiac monitoring, should occur on the same day as the core study FU1 or abbreviated FU2 (whichever applies). In all cases, all assessments and procedures of Visit 1 must be completed (i.e., study treatment start) no longer than 7 days after signing of the informed consent (start of Visit 1).

The time from last dose of study treatment in the OPTIMUM study to the first dose of ponesimod in this study will last at least 14 days, but can last up to 44 days. The investigator should make every effort to minimize the duration of the treatment interruption between EOT of the core study and Day 1 of the extension study. Ideally, the treatment interruption should not last longer than 15 days.

The treatment period consists of 240 weeks of treatment with ponesimod including a 14-day gradual up-titration beginning on Day 1, followed by daily treatment with 20 mg ponesimod.

15 March 2022, page 51/216

Confidential

EudraCT 2016-004719-10 EDMS-ERI-207656619

Treatment will stop before 240 weeks if ponesimod becomes commercially available for the treatment of multiple sclerosis in the subject's country.

The visits during the treatment period will consist of an enrollment visit; three visits at 2 (i.e., 15 days), 4, and 12 weeks after enrollment; and visits every 12 weeks thereafter until the EOT.

The treatment period may include a study treatment interruption period of variable duration [see Section 5.1.12]. The permitted maximum duration of the study treatment interruption is 81 weeks for planned pregnancies and 12 weeks for other reasons (if exceeded, then the subject will be prematurely discontinued from the study). During the treatment interruption the subject will follow the planned visit schedule off-treatment with the corresponding assessments with exceptions of assessments that are contra-indicated due to the subject's condition (e.g., in the event of pregnancy, scheduled MRI assessments will not be performed).

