6.2 Safety endpoints

In order to investigate the long-term safety of ponesimod and the changes in safety in teriflunomide subjects switching to ponesimod 20 mg, analysis will be performed on all data in the core and extension studies combined, using the core baseline as a reference. In addition, safety data

15 March 2022, page 87/216

reference.

EudraCT 2016-004719-10 EDMS-ERI-207656619

Confidential

collected in the extension study will be analyzed independently, using the extension baseline as a

Table 9 details which endpoints will be analyzed for the Extension Analysis Period, and which for the Combined Analysis Period.

Table 9 Analysis of safety endpoints

Endpoints	Combined Analysis Period	Extension Analysis Period
Adverse events		
 Treatment-emergent AEs, SAEs, and AEs of special interest[#] AEs leading to premature discontinuation of study treatment 	Y* Y	Y Y
Cardiac safety		
• Treatment-emergent morphological ECG abnormalities (as defined by the ECG provider)	Y*	Y
 Absolute values by visit for 12-lead ECG parameters (HR, PR, QRS, QT, QTcB, QTcF) 	Y	Y
 Change from baseline values by visit for ECG parameters (HR, PR, QRS, QT, QT QTcB, QTcF) 	Y	Y
 Change in ECG parameters (HR, PR, QRS, QT, QT QTcB, QTcF) from pre-dose to selected post-dose assessments (1 h, 2 h, 3 h, 4 h) on Day 1 and on day of re-initiation of study treatment 	N	Y
Pulmonary safety		
• Absolute values and percent change from baseline in FEV ₁ and FVC at all assessments	Y	Y
• Treatment-emergent decrease from baseline $>20\%$ and $>30\%$ in FEV ₁ or FVC	Y	Y
• Treatment-emergent decrease from baseline >20 percentage points in % of predicted FEV ₁ and FVC	Y	Y
• Among subjects with a decrease of ≥ 200 mL or $\geq 12\%$ in FEV ₁ or FVC from baseline to EOT, reversibility defined as a decrease of < 200 mL or $< 12\%$ in FEV ₁ or FVC from baseline to EOS**	Y	N

15 March 2022, page 88/216

EudraCT 2016-004719-10 EDMS-ERI-207656619

Confidential

Table 9

Analysis of safety endpoints

Endpoints	Combined Analysis Period	Extension Analysis Period
 Absolute change from baseline to EOS versus change from baseline to EOT in FEV₁ and FVC (absolute and % of predicted)** 	Y	N
• Change in lung diffusion capacity as assessed by DL _{CO} (at selected sites only) expressed in absolute change (mL) and % of predicted value from baseline at all assessments	Y	Y
• Change from baseline to EOS versus change from baseline to EOT in DL _{CO} (absolute and % of predicted) (at selected sites only)**	Y	N

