8.4.1 EOS Visit

This visit will be conducted 30–44 days after the permanent discontinuation of study treatment. All assessments should be conducted within the visit window. The last assessment conducted for the study will define the visit date.

The EOS visit should also be conducted for subjects who have switched to commercially available ponesimod.

The visits include:

- EDSS/FS
- MS relapse
- Recording of changes in concomitant medications
- Assessment and recording in the eCRF of methods of contraception (for WOCBP only)
- Body temperature
- SBP/DBP
- 12-lead ECG
- Ophthalmological examination (under the responsibility of the ophthalmologist)
- OCT (under the responsibility of the ophthalmologist)⁶
- Spirometry
- DL_{CO} (if applicable; under the responsibility of the pulmonologist)
- Hematology, blood chemistry, and (following approval of protocol version 5) a serum sample for immunogenicity evaluations (e.g., anti SARS-CoV-2 antibody testing) will be collected for all subjects
- Urinalysis
- Serum pregnancy test for WOCBP
- Recording of AEs and SAEs
- Remind WOCBP and fertile men to use the methods of contraception defined for this study until 6 weeks after the first of two consecutive tests confirming plasma teriflunomide level <0.02 mg/L[#] if such test results have not been obtained prior to EOS visit.

Important note: Teriflunomide testing is no longer required with the approval of protocol version 5

Scheduled OCT assessments are only applicable to Global Protocol version 1 to 5. The requirement for OCT assessments was removed from Protocol Version 6 onwards.

EudraCT 2016-004719-10 EDMS-ERI-207656619

Confidential

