11.1.2 Analysis strategy for safety

The long-term safety of ponesimod and the changes in safety in teriflunomide 14 mg subjects switching to ponesimod 20 mg will be investigated by summarizing the combined data from both the core and extension studies. Cumulative data such as AEs and SAEs will only be summarized for subjects initially treated with ponesimod 20 mg in the core study to allow a long-term assessment of up to 6 years. To assess trends over time and to assess the switch from teriflunomide 14 mg to ponesimod 20 mg, the analysis of the change from baseline for safety endpoints will be assessed by visit from core baseline up to last treatment + 15 days, and will be analyzed by core treatment group.

In addition, all safety data collected in the extension study will be analyzed for the extension study only, and will be summarized both overall and split by the core treatment group. For this analysis, the extension study baseline is used as the reference.

Section 6.2 details which safety endpoints will be analyzed for the combined core and extension studies, and which will be analyzed for the extension study.

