11.1.3 Baseline definitions

The following baseline definitions will be used:

- The core baseline value for efficacy is defined as the last non-missing value recorded before randomization in the core study for each endpoint and each subject individually.
- The core baseline value for safety is defined as the last non-missing value recorded before the
 first study treatment administration in the core study for each endpoint and each subject
 individually.

Confidential

EudraCT 2016-004719-10 EDMS-ERI-207656619

• The extension baseline value for efficacy and safety is defined as the last non-missing value recorded in either the core or extension studies before the first administration of ponesimod in the extension study (unless otherwise specified in the SAP).

Analysis over the Extension Analysis Period will use the extension study baseline, whilst analysis over the Combined Analysis Period will use the core study baseline.

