11.4.8.3.3 Reversibility of treatment-emergent decreases in FEV₁ and FVC

For the subset of subjects with a decrease of ≥200 mL or ≥12% in FEV1 or FVC from core baseline at EOT, the number and percentage of subjects with a decrease of <200 mL and <12% from core baseline to EOS** in FEV1 or FVC will be summarized for subjects who received ponesimod 20 mg in the core study only for the Combined Analysis Period using the SAF.

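### The FEV1/FVC reversibility count compares raw volumes with a core baseline up to about 6.8 years old, so age-related loss biases it toward non-reversal in long-followed subjects

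*Protocol*

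**What the plan says.** Section 11.4.8.3.3 of the protocol builds the count in two steps. Entry: "For the subset of subjects with a decrease of ≥200 mL or ≥12% in FEV1 or FVC from core baseline at EOT". Reversal: at EOS the fall from core baseline is below 200 mL *and* below 12%. The count covers only subjects given ponesimod 20 mg in the core study, and leaves out those exposed to commercial ponesimod before EOS.

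Table 9 (section 6.2) lists the same endpoint: "or FVC from baseline to EOT, reversibility defined as a decrease of" less than 200 mL *or* less than 12%. It is marked for the Combined Analysis Period and not for the Extension Analysis Period, so no version uses the extension baseline.

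Section 11.1.3 fixes the reference: "The core baseline value for safety is defined as the last non-missing value recorded before" the first core dose. On the EOS visit, section 8.4.1 says: "This visit will be conducted 30–44 days after the permanent discontinuation of study treatment". Section 11.1.2 describes the combined follow-up as intended "to allow a long-term assessment of up to 6 years".

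**The concern.** The count is the only display that says how many subjects recover lung volume after stopping ponesimod. Entry and reversal are both judged against one old value, on a scale that drifts down with age. Age-related loss helps a subject into the subset at EOT. It is still there at EOS, because a few weeks off drug cannot undo years of ageing. Both effects push the same way and grow with time on study. A fully reversible drug effect could then look largely irreversible in the subjects followed longest, who are the ones a long-term extension exists to inform.

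**Working it through.** **Age of the baseline.** Three inputs are needed.

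- Core treatment is 108 weeks (section 3.1: "Subjects who have completed the 108-week treatment period in the core study").
- Extension treatment is at most 240 weeks (section 3.2.3: "The treatment period consists of 240 weeks of treatment with ponesimod").
- The gap between the two "will last at least 14 days, but can last up to 44 days" (section 3.2.3).

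Treatment time alone is (108 + 240) × 7 / 365.25 = 2436 / 365.25 = 6.67 years. That is 11% above the stated 6 years (6.67 / 6 = 1.11), which looks like rounding down and is not raised as an error.

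- EOT with the gap: (2436 + 14) / 365.25 = 6.71 to (2436 + 44) / 365.25 = 6.79 years.
- EOS, 30 to 44 days after the last dose: (2450 + 30) / 365.25 = 6.79 to (2480 + 44) / 365.25 = 6.91 years.
- Core-only subjects: 756 / 365.25 = 2.07 years at EOT.

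**Which limit governs.** The 12% limit is easier to meet than 200 mL only if baseline is below 200 / 0.12 = 1667 mL. For most adults the 200 mL limit decides.

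**Ageing against 200 mL.** The protocol gives no ageing rate, so 15 to 35 mL/year is an assumption. Over 6.67 years, 15, 20, 25, 30 and 35 mL/year give 100, 133, 167, 200 and 233 mL. The break-even rate is 200 / 6.67 = 30.0 mL/year for a full-length subject, inside the assumed range. At 2.07 years it is about 96.6 mL/year, far outside it.

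**Simulation of the rule with no drug effect.** All inputs are assumed: baseline mean 3.2 L (SD 0.6 L), between-subject SD of the ageing slope 15 mL/year, visit error SD 100 mL, 400,000 subjects per setting, one lung measure. Results at 6.67 years:

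| Mean ageing, mL/year | Qualify at EOT | Reversed, *and* rule | Reversed, *or* rule |
|---|---|---|---|
| 15 | 28% | 39% | 83% |
| 20 | 35% | 35% | 80% |
| 25 | 42% | 30% | 77% |
| 30 | 50% | 26% | 72% |
| 35 | 58% | 22% | 68% |
| Average ageing subtracted | 12% | 53% | not computed |

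At 2.07 years, 12 to 19% qualify, against 8% with average ageing subtracted.

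A second set-up (SD of change between two tests 150 mL, no slope variation, 6.79 years) agrees. With no ageing, 9% qualify and 69% of them count as reversed. At 15 to 35 mL/year, 26 to 60% qualify and 51 to 27% count as reversed under the *and* rule.

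**With a fully reversible 150 mL drug effect** (first set-up, 6.67 years), the *and* rule reports 58 to 34% reversed on raw volumes and 72 to 73% with average ageing subtracted.

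***And* against *or*.** Take a 3.0 L baseline and a value 250 mL lower at both EOT and EOS. The fall is at least 200 mL, so the subject enters. Since 12% of 3.0 L is 360 mL and 250 < 360, the Table 9 wording counts the subject as reversed although nothing changed. Section 11.4.8.3.3 does not.

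**The case against.** The strongest reply is that the protocol already shows reversibility in ways that ageing hardly touches. Section 11.4.8.3.1 plots mean change to EOT and to EOS in mL, percent and % predicted, by core arm. Both changes share one baseline, so the EOT-to-EOS contrast carries at most about 35 × 44 / 365.25 = 4 mL of ageing. Section 11.4.8.3.2 counts decreases in % predicted. Table 9 lists EOS-versus-EOT change as absolute and % predicted, and also gives the decrease endpoints for the Extension Analysis Period. This stands: a reader might infer that lung-function decline is misjudged throughout, and the documents do not support that. Even the raw 20% limit in Table 9 is 640 mL at 3.2 L, well beyond the ageing computed here. What remains is that mean plots do not say how many subjects reversed. The % predicted displays also remove ageing only if predicted values use the age at each visit, which the protocol does not state.

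A reader might also infer that a control arm was left out, or that ageing is labelled drug-related. Neither holds. Everyone in the extension takes ponesimod, so no drug-free group exists at extension EOT. The protocol's term is treatment-emergent, and section 11.4.1 pre-specifies no hypotheses.

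Finally, the interval used is the maximum. The Safety Set includes core-only subjects, treatment can end early, and under the *or* wording the reversed share is much higher. All of this is correct and limits the size of the point.

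**Conclusion.** The point holds for one endpoint: the categorical reversibility count in 11.4.8.3.3 and its Table 9 row. In subjects followed for most of the planned duration, the stated rule biases that count toward non-reversal. The direction needs only that lung volumes fall with age and do not recover in 30 to 44 days. The size depends on an ageing rate and test variability that the protocol does not give, so the simulated shares are illustrations. They also cover one lung measure, while the rule accepts FEV1 or FVC.

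The bias is substantial at 6.67 years under the *and* rule, smaller under *or*, and modest at 2.07 years. The conflict between *and* and *or* needs no assumption. Because the analysis is descriptive and less affected displays stand beside it, the severity is minor.

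**What to change.** In 11.4.8.3.3 and the matching row of Table 9:

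- Add the same count on an age-adjusted scale: observed minus predicted volume, or % predicted. State the reference equations, and that predicted values are computed at the subject's age at each visit.
- Base the interpretation of reversibility on that version and keep the raw count alongside it.
- Use one reversal definition in both places. The *and* form is the exact complement of the entry rule; the *or* form overlaps with it.
- Make the population the same in both places, since the Table 9 row does not carry the mark that limits other rows to core-ponesimod subjects.

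The cost is one derived variable and a wording change. % predicted is already planned, so no new data are needed. There are two small downsides. The result depends on how well the reference equations track ageing in this population. And a limit of 12 percentage points of % predicted is not the same as 12% of baseline volume: for a subject at 80% of predicted, 12% of baseline is 0.12 × 80 = 9.6 percentage points. The chosen limit should therefore be written out.

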Other endpoints		
 Absolute values and change from baseline for HR, SBP, DBP and body weight at all assessments 	Y	Y
• Treatment-emergent notable blood pressure abnormalities##	Y	Y
 Absolute values and change from baseline for laboratory tests (hematology, blood chemistry, urinalysis) at all assessments 	Y	Y
• Treatment-emergent notable laboratory abnormalities##	Y	Y
 Change from baseline to EOS versus change from baseline to EOT in lymphocyte counts (absolute and percent change)** 	Y	N
• Treatment-emergent eC-SSRS suicidal ideation score of 4 or above, or a "yes" response on the eC-SSRS suicidal behavior item	Y	N

Cumulative safety data, i.e., AEs for the combined analysis period will only be presented for subjects who received 20 mg ponesimod in the core study.

The selection of AEs of special interest [see Appendix 4] is based on the anticipated risks of treatment with ponesimod; the final list of AEs of special interest will be defined in the SAP.

The selection of notable abnormalities considered for the analyses is based on standard definitions and the anticipated risks of treatment with ponesimod; the final list of abnormalities will be defined in the SAP.

^{**} Only for subjects who have no exposure to commercially available ponesimod prior to the EOS visit.

AE = adverse event; DBP = diastolic blood pressure; DL_{CO} = diffusing capacity for the lungs measured using carbon monoxide; eC-SSRS = electronic self-rated version of the Columbia-Suicide Severity Rating Scale; ECG = electrocardiogram; EOS = End-of-Study; EOT = End-of-Treatment; FEV_1 = forced expiratory volume in 1 second; FVC = forced vital capacity; HR = heart rate; QTcB = QT corrected for heart rate on the basis of Bazett's formula; QTcF = QT corrected for heart rate on the basis of Fridericia's formula; SAE = serious adverse event; SAP = statistical analysis plan; SBP = systolic blood pressure.

15 March 2022, page 89/216

Confidential

EudraCT 2016-004719-10 EDMS-ERI-207656619

The treatment-emergent period is defined as the time from first ponesimod administration in the applicable Analysis Period up to 15 days (inclusive) after last study treatment administration. This definition applies regardless of whether the subject receives commercially available ponesimod after completing study treatment.

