11.4.8.3.2 Treatment-emergent decreases in FEV₁ and FVC

The number and proportion of treatment-emergent decreases of % of predicted FEV_1 or FVC > 20 percentage points from core baseline at any time during the Combined Analysis Period for subjects who received ponesimod 20 mg in the core study based only on the SAF will be summarized in a similar manner to the AEs as described in Section 11.4.8.1.1.

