11.4.8.5 Laboratory endpoints

Descriptive summary statistics by visit will be provided for observed treatment-emergent values and absolute change from core baseline for laboratory tests (hematology, blood chemistry, urinalysis) by core study treatment for the Combined Analysis Period using the SAF. These parameters will also be summarized descriptively for the Extension Analysis Period by core study treatment and overall using the EXTS.

Treatment-emergent laboratory notable abnormalities will be summarized for subjects who received ponesimod 20 mg in the core study only for the Combined Analysis Period using the SAF.

The definition for notable abnormalities is provided in Appendix 5 and include:

- Treatment-emergent laboratory test abnormalities based on normal ranges of the central laboratory, project-specific ranges, and common terminology criteria for adverse events (CTCAE) [CTCAE 2010; see Appendix 5]
- Treatment-emergent laboratory test abnormalities based on FDA guidance for DILI [FDA 2009b] (for ALT / AST / total bilirubin).

Lymphocyte count reversibility after EOT will be summarized descriptively by comparing the mean (and 95% CIs) for absolute change in lymphocyte counts from core baseline to EOS, and from core baseline to EOT.** This analysis will be performed for the Combined Analysis Period by core study treatment using the SAF.

** applies only to subjects who have no exposure to commercially available ponesimod prior to the EOS visit.

11.4.8.6 eC-SSRS

The number and percentage of subjects with a treatment-emergent eC-SSRS suicidal ideation score of 4 or above, or a "yes" response on the eC-SSRS suicidal behavior item will be summarized descriptively by core study treatment for the Combined Analysis Period.

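### Table 9 plans categorical FEV1/FVC reversibility with no core-ponesimod limit, but section 11.4.8.3.3 imposes one, so switchers get no responder count in either period, and the two places define reversal differently

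*Protocol*

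**What the plan says.** Protocol section 6.2 gives as one purpose of the combined safety analysis "the changes in safety in teriflunomide subjects switching to ponesimod 20 mg". Table 9 then marks each endpoint Y or N for the Combined and Extension Analysis Periods. A single asterisk limits a Combined Period entry to core-ponesimod subjects; its footnote begins "Cumulative safety data, i.e., AEs for the combined analysis period will only be presented for". Two rows carry it: the row for treatment-emergent AEs, SAEs and AEs of special interest, and the row for morphological ECG abnormalities.

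The categorical reversibility row starts from subjects whose FEV1 or FVC has fallen by at least 200 mL or at least 12% at EOT. It has "reversibility defined as a decrease of" less than 200 mL *or* less than 12% at EOS. It is Y for the Combined Period with no single asterisk, and N for the Extension Period. Its double asterisk only excludes subjects who took commercial ponesimod before EOS. The next row, "Absolute change from baseline to EOS versus change from baseline to EOT in" FEV1 and FVC, is coded the same way.

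Section 11.4.8.3.3 takes the same starting subset, requires less than 200 mL *and* less than 12% at EOS, and states that the count "will be summarized for subjects who received ponesimod 20 mg in the core study only for the Combined Analysis Period using the SAF".

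Two other rows have a similar mismatch. The row "Treatment-emergent decrease from baseline >20 percentage points in % of predicted" FEV1 and FVC and the row for notable laboratory abnormalities are Y for both periods with no asterisk. Section 11.4.8.3.2 summarises the first "for subjects who received ponesimod 20 mg in the core study based only on the SAF". Section 11.4.8.5 says: "Treatment-emergent laboratory notable abnormalities will be summarized for subjects who received ponesimod 20 mg in the core study only".

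**The concern.** The protocol fixes the population for one endpoint twice, in two different ways. For most rows a second analysis in the Extension Period would soften this, but categorical reversibility has none. If section 11.4.8.3.3 is followed, the question of what share of subjects with a marked fall in lung function recovered after stopping ponesimod is answered only for those who began ponesimod in the core study. The first safety objective (section 2.1) concerns ponesimod 20 mg in subjects with RMS generally, and section 6.2 names the switchers explicitly.

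The difference between *or* and *and* changes which subjects count as recovered, so the reported percentage depends on which section the programmer follows.

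**Working it through.** The plan states no figure for this point, so the check is a comparison of passages plus a short piece of logic on the definition.

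**1. Coverage of switchers, row by row**

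| Endpoint | Table 9, Combined | Table 9, Extension | Section 11, Combined Period | Switchers covered? |
|---|---|---|---|---|
| Categorical reversibility | Y, no single asterisk | N | Core-ponesimod only (11.4.8.3.3) | In neither period |
| Mean change to EOS versus EOT, FEV1 and FVC | Y | N | By core treatment (11.4.8.3.1) | Yes |
| Lymphocyte change to EOS versus EOT | Y | N | By core treatment (11.4.8.5) | Yes |
| Fall of more than 20 percentage points in % predicted | Y, no asterisk | Y | Core-ponesimod only (11.4.8.3.2) | Extension Period, under 11.4.8 |
| Notable laboratory abnormalities | Y, no asterisk | Y | Core-ponesimod only (11.4.8.5) | Extension Period, under 11.4.8 |

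Only the first row leaves switchers with nothing. The two parallel EOT-to-EOS analyses are both by core treatment, so section 11.4.8.3.3 is the exception, and it gives no reason.

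**2. Are the data there?** Yes. Sections 8.3.10 and 8.4.1 list spirometry at the EOT and EOS visits for every extension subject, with no distinction by core arm.

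**3. The definition of reversal.** Let d be the fall in mL and p the fall in percent from core baseline, for one parameter.

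- Qualifying at EOT (both places): d ≥ 200 or p ≥ 12.
- Its logical complement: d < 200 and p < 12. This is the definition in section 11.4.8.3.3.
- Table 9: d < 200 or p < 12. This overlaps the qualifying set.

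Take a fall of 250 mL and 8% at EOT, unchanged at EOS. The implied baseline is 250 / 0.08 = 3,125 mL. The subject qualifies because 250 ≥ 200. Under Table 9 the subject is reversed because 8 < 12. Under section 11.4.8.3.3 the subject is not reversed because 250 is not below 200.

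For that baseline, 12% is 0.12 × 3,125 = 375 mL. Any stable fall from 200 mL to just under 375 mL therefore qualifies and is counted as reversed under Table 9 with no recovery at all. The overlap vanishes only where 200 mL equals 12%, at a baseline of 200 / 0.12 = 1,667 mL. Everyone who meets the *and* definition also meets the *or* definition, so Table 9 can only raise the reversal percentage.

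**4. Size of the affected group.** The denominator is switchers with a qualifying fall at EOT and no commercial ponesimod before EOS. The protocol gives neither quantity.

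**The case against.** The strongest defence is that the limit is deliberate. Sections 11.1.2 and 11.4.8 restrict cumulative data, such as AEs and SAEs, to core-ponesimod subjects. Section 10.1.1 defines treatment-emergence in the Combined Period from the first ponesimod dose in the core study, which switchers never had, and a switcher's fall from core baseline could have arisen on teriflunomide. Table 9's asterisks are also not a dependable guide: AEs leading to discontinuation carry a plain Y for the Combined Period, although the footnote restricts AEs. On this view the error is a few missing asterisks.

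For counts of events at any time this largely stands, and adding asterisks to the percentage-point and laboratory rows is a fair repair. It does not carry over to reversibility, which compares two visits around the stopping of ponesimod and is not a cumulative count. A split by core arm also deals with the concern about earlier teriflunomide exposure.

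A reader might infer four stronger things that the protocol does not support:

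- **That switchers' lung reversibility is never analysed.** Section 11.4.8.3.1 plots mean FEV1 and FVC change, with 95% CIs, to EOT and to EOS by core treatment. What it cannot show is the share of subjects with a qualifying fall who recovered.
- **That falls and laboratory abnormalities are unplanned for switchers in the Extension Period.** Table 9 gives them Y, and section 11.4.8 summarises the EXTS overall and by core arm. Section 11.4.8.3.2 also restricts only the percentage-point row; Table 9's >20% and >30% falls are not named there.
- **That Table 9 requires both FEV1 and FVC to fall by more than 20 percentage points.** The phrase can simply list two parameters, and the heading and body of section 11.4.8.3.2 mix *and* and *or* for one analysis.
- **That about 400 subjects are lost (half of about 800 entrants) and the CI is 1.4 times wider.** The denominator is subjects with a qualifying fall at EOT, not all entrants.

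**Conclusion.** The point holds for categorical FEV1/FVC reversibility. Table 9 and section 11.4.8.3.3 contradict each other on who is counted and on what counts as reversed. Following section 11.4.8.3.3, switchers have no responder-type reversibility result in either period, which sits badly with the stated aim of describing safety after the switch. Following Table 9's definition, some subjects with no recovery are counted as recovered.

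The consequence is bounded. The study is descriptive with no pre-specified hypotheses (section 11.4.1), switchers keep the mean-change plot, and no decision rule depends on the count. The loss of precision cannot be quantified because the number of switchers with a qualifying fall is not given. For the percentage-point and laboratory rows this is a labelling mismatch only. These conclusions rest on reading the single asterisk as the mark for the core-ponesimod limit, which is how the footnote and the two marked rows fit together.

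**What to change.** - **Section 11.4.8.3.3:** summarise categorical reversibility by core arm and overall for all subjects treated with ponesimod who have a qualifying fall at EOT and no commercial ponesimod before EOS. For switchers, use the extension EOT and EOS visits. Core-teriflunomide subjects who never entered the extension stay out, since they never took ponesimod.
- **Definition:** use below 200 mL *and* below 12% in both Table 9 and section 11.4.8.3.3, so that reversal is the complement of the qualifying fall.
- **Table 9:** for the percentage-point and notable laboratory abnormality rows, align the Combined Period asterisks with sections 11.4.8.3.2 and 11.4.8.5. The Extension Period summaries by core arm need no change.

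The cost is wording in the protocol or SAP and a few table columns. No new data are needed.
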